11.2. Appendix 2: Assessment Windows

11.2.1. Definitions of Assessment Windows for Analyses

Analysis Set / Domain	Parameter (if applicable)	Target	Analysis Window		Analysis Timepoint
			Beginning Timepoint	Ending Timepoint	
All	All	Nominal Day	Nominal day – 1 days	Nominal day + 1 days	Visits for Day 14, Day 21 and Week 4 telephone call
All	All	Nominal Day	Nominal day –3 days	Nominal day +3 days	Visits from Week 6 to Month 3
All	All	Nominal Day	Nominal day –7 days	Nominal day +7 days	Visits from Month 6 to Month 24
Safety/PK/CD 3	All	In Window	-5 minutes predose	0 minutes predose	Predose
Safety/PK/CD 3	All	Nominal time point	Nominal time point	+5 minutes	Any postdose up to 6h
Safety/PK/CD 3	All	Nominal time point	Nominal time point	+10 minutes	Any postdose after 6h

Analysis Timepoint will be defined based on the nominal visit label, however a flag will be derived if a visit is considered outside of assessment window. Visits out of window will be included in all analyses but will be flagged in the listings. Sensitivity analyses may be performed excluding these visits.

11.3. Appendix 3: Study Phases

11.3.1. Study Phases

Assessments and events will be classified according to the time of occurrence relative to dosing.

Study Phase	Definition
Pre-Treatment	Date < Date of First Dose
During Dosing	Date of First Dose <= Date <= Date of Final Dose + 1.
Post-dose to Week 6	Date of Final Dose + 1 < Date <= Date of Week 6 Visit ^[1] or Day 42 whichever is greater
Week 6 to Month 24	Date of Week 6 Visit ^[1] or Day 42 whichever is greater < Date <= Month 24 visit.
Safety Follow-up	Date > Month 24
[1] For participants who were consented Prior to Protocol Amendment 4, Day 42 will be used, as they will not have a Week 6 visit.	

Note: for any rule that is relative to dose, the term date also includes time, if recorded. The end date for a visit as recorded in the SV domain will be used for the determining study phase.

11.3.1.1. Study Phases for Concomitant Medication

Study Phase	Definition
Prior	If medication end date is not missing and end date is prior to dosing
Concomitant	Any medication that is not a prior

NOTES:

- Please refer to Section 11.6 Premature Withdrawals & Handling of Missing Data for handling of missing and partial dates for concomitant medication. Use the rules in this table if concomitant medication date is completely missing.

11.4. Appendix 4: Data Display Standards & Handling Conventions

11.4.1. Derivations and Handling of Missing Baseline Data

Definition	Reporting Details
Change from Baseline	= Post-Dose Visit Value – Baseline
% Change from Baseline	= 100 x [(Post-Dose Visit Value – Baseline) / Baseline]
Ratio to Baseline*	= Post-dose Visit Value / Baseline

NOTES :

- Unless otherwise specified, the baseline definitions specified in Section 5.2 Baseline Definitions will be used for derivations for endpoints / parameters and indicated on summaries and listings.
- Unless otherwise stated, if baseline data is missing no derivation will be performed and will be set to missing.
- * only generated for strictly >0 parameters.

11.4.2. Reporting Process

Reporting Process	
Software	

 • The currently supported versions of SAS will be used to perform all data analyses and generation of displays (tables, figures, and listings). 	
Reporting Area (GSK)	
➤ HARP Server	UK1SALX00175
➤ HARP Area	\\arwork\gsk2136525\otx116505\[reporting effort] \\arprod\gsk2136525\otx116505\[reporting effort]
Reporting Area (PXL)	
➤ PXL Server	Kennet
➤ SDTM Data	Transfer folder on Kennet
➤ ADaM Data	Location: [project folder on kennet] /stats/nonversioncontrol/primary/data/sas/derived/main
➤ Programmed TLFs	Location: [project folder on kennet] /stats/nonversioncontrol/primary/output/final
Analysis Datasets	

 ➤ Analysis datasets will be created according to CDISC / ADaM Standards Library standards. ➤ Define version 2.0 will be used for the SDTM datasets ➤ Define version 2.0 will be used for the analysis datasets. 	
Generation of RTF Files	

 • RTF files will be generated for the final reporting effort. 	

11.4.3. Reporting Standards

Reporting Standards	
General	

 • The current GSK Integrated Data Standards Library (IDSL) will be applied for reporting, unless otherwise stated: 
 ○ 4.03 to 4.24: General Principles ○ 5.01 to 5.08: Principles Related to Data Listings ○ 6.01 to 6.11: Principles Related to Summary Tables ○ 7.01 to 7.13: Principles Related to Graphics 	
Formats	

 • GSK IDSL Statistical Principles (5.03 & 6.06.3) for decimal places (DP's) will be adopted for reporting of data based on the raw data collected, unless otherwise stated. • Numeric data will be reported at the precision collected on the eCRF. • The reported precision from non eCRF sources will follow the IDSL statistical principles but may be adjusted to a clinically interpretable number of DP's. 	
Planned and Actual Time	

 • Reporting for tables, figures and formal statistical analyses: 
 • Planned time relative to dosing will be used in figures, summaries, statistical analyses and calculation of any derived parameters, unless otherwise stated. • The impact of any major deviation from the planned assessment times and/or scheduled visit days on the analyses and interpretation of the results will be assessed as appropriate. • Reporting for Data Listings: 
 • Planned and actual time relative to study drug dosing will be shown in listings (Refer to IDSL Compiled Statistical Principle 5.05.1). • Unscheduled or unplanned readings will be presented within the participant's listings. 	
Unscheduled Visits	

 • Unscheduled visits will not be included in summary tables or figures. • All unscheduled visits will be included in listings. 	
Descriptive Summary Statistics	
Continuous Data	Refer to IDSL Statistical Principle 6.06.1
Categorical Data	N, n, frequency, %
Graphical Displays	

 • Refer to IDSL Compiled Statistical Principles 7.01 to 7.13. 	

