5.2. Baseline Definitions

For all endpoints (except as noted in baseline definitions) the baseline value will be the latest pre-dose assessment with a non-missing value, including those from unscheduled visits. If time is not collected, Day 1 assessments are assumed to be taken prior to first dose and used as baseline.

Unless otherwise stated, if baseline data is missing no derivation will be performed and baseline will be set to missing.

As triplicates are taken for the baseline ECG data, the average will be used as baseline. If one or two of the triplicate measurements are missing, the remaining measurement(s) will be used to calculate the average. For categorical variables for triplicate ECG assessments the worst case will be used. In terms of worseness this is defined as abnormal, clinically significant > abnormal, clinically insignificant > normal > unable to evaluate.

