11.5. Appendix 5: Derived and Transformed Data

11.5.1. General

Multiple Measurements at One Time Point

 • Mean of the measurements will be calculated and used in any derivation of summary statistics but if listed, all data will be presented, including the mean. • The nominal time point will be used as described in Section 11.2. • Participants having both High and Low values for Normal Ranges at any post-baseline visits for safety parameters will be counted in both the High and Low categories of “Any visit post-baseline” row of related summary tables. This will also be applicable to relevant Potential Clinical Importance summary tables.
Study Day

 • Calculated as the number of days from randomisation date : 
 • Ref Date = Missing → Study Day = Missing • Ref Date < Randomisation Date → Study Day = Ref Date – Randomisation Date • Ref Date ≥ Randomisation Date → Study Day = Ref Date – (Randomisation Date) + 1

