2.14.	Safety	LB1	Summary of Laboratory Changes from Baseline	
 Order parameters alphabetically BY Labtype (1. Chemistry, 2. Haematology) 	FA (SAC)
2.15.	Safety	LB15	Summary of Worst Case Laboratory Results Relative to Normal Range Post-Baseline Relative to Baseline	
 Order parameters alphabetically BY Labtype (1. Chemistry, 2. Haematology) 	FA (SAC)
Electrocardiograms					
2.16.	Safety	EG1	Summary of ECG Findings		FA (SAC)
2.17.	Safety	EG2	Summary of Change from Baseline in ECG Values		FA (SAC)
2.18.	Safety	EG10	Summary of Maximum QTc Values Post-Baseline Relative to Baseline by Category		FA (SAC)
2.19.	Safety	EG11	Summary of Maximum Increase in QTc Values Post-Baseline Relative to Baseline by Category		FA (SAC)
Vital Signs					
2.20.	Safety	VS1	Summary of Change from Baseline in Vital Signs		FA (SAC)
2.21.	Safety	VS7	Summary of Worst Case Vital Sign Results Relative to Potential Clinical Importance (PCI) Criteria Post-Baseline Relative to Baseline		FA (SAC)

Immunogenicity					
2.22.	Safety	Non-Standard EFF_T4	Summary of Immunogenicity	
 With positive instead of responder 	FA (SAC)

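### SAP 11.4.3 keeps unscheduled visits out of every summary table, so the worst-case and maximum safety tables (2.15, 2.18, 2.19, 2.21) can only equal or understate the recorded extreme

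*SAP*

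**What the plan says.** SAP 11.4.3 (Reporting Standards) states: "Unscheduled visits will not be included in summary tables or figures". Its next line sends unscheduled visits to the listings.

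SAP 11.10.5 lists four tables of extremes:

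- Table 2.15: "Summary of Worst Case Laboratory Results Relative to Normal Range Post-Baseline Relative to Baseline"
- Table 2.18: "Summary of Maximum QTc Values Post-Baseline Relative to Baseline by Category"
- Table 2.19: "Summary of Maximum Increase in QTc Values Post-Baseline Relative to Baseline by Category"
- Table 2.21: "Summary of Worst Case Vital Sign Results Relative to Potential Clinical Importance (PCI) Criteria Post-Baseline Relative to Baseline"

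The programming notes for 2.15 cover only parameter order and laboratory type. The other three have none.

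Three other rules bear on the point:

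- SAP 5.2, on baseline: "the baseline value will be the latest pre-dose assessment with a non-missing value, including those from unscheduled visits".
- SAP 11.5.1, on High and Low counts: "Participants having both High and Low values for Normal Ranges at any post-baseline visits for safety parameters will be counted in both" categories of the any-visit row.
- SAP 11.2.1, on time points: "Analysis Timepoint will be defined based on the nominal visit label".

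SAP 7.5 and 7.6 refer laboratory, ECG and vital-sign analyses to the sponsor's core data standards and do not mention unscheduled visits.

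**The concern.** Leaving unscheduled visits out of by-visit means is sound, since such values belong to no planned time point and are often taken because something looked abnormal. For a table of extremes the same feature argues the other way: values obtained because of a concern are among those most likely to be extreme.

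A patient whose first out-of-range result, first vital sign of potential clinical importance or highest QTc category falls at an unscheduled visit would be shown by milder scheduled values. Safety is the primary objective, and changes in laboratory values, ECGs and vital signs form one of its endpoints. A reader of a table titled worst case or maximum would not expect recorded values to be missing from it.

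The plan is also uneven. Within one table an unscheduled value may set the baseline but may not count after dosing. The any-visit wording of 11.5.1 leaves two programmers free to build those rows differently.

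**Working it through.** The documents give no figure to reproduce, so the check has four parts.

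**1. Does any text lift the exclusion?** SAP 11.4.3 applies the reporting standards library only where the SAP does not state otherwise, and here it does. SAP 7.5 and 7.6 are silent on unscheduled visits. SAP 11.5.1 speaks of any post-baseline visit, but it is a double-counting rule and does not name unscheduled visits. SAP 11.2.1 keeps out-of-window visits, which is a different matter. SAP 11.6.1 admits only planned data to tables for withdrawn participants, which agrees with the exclusion. No exception was found.

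**2. Direction.** Let S be a patient's scheduled post-baseline values and A all recorded post-baseline values, so that S is contained in A. Then:

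- max(S) ≤ max(A) and min(S) ≥ min(A);
- with the baseline b fixed, max(S) − b ≤ max(A) − b.

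Illustration with assumed values: baseline QTc 420 msec, scheduled values 430, 445 and 448, one unscheduled value 505.

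| | Scheduled only | All values | SAP 11.7.2 limit |
|---|---|---|---|
| Maximum QTc (msec) | 448 | 505 | >450 |
| Maximum increase (msec) | 448 − 420 = 28 | 505 − 420 = 85 | >60 |

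Under the current rule this patient passes neither limit in Tables 2.18 and 2.19, yet appears in the ECG listings of potential clinical importance.

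**3. Can tests fall on dates with no scheduled visit?**

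- *Liver tests.* Protocol 6.2.2 footnote 8 calls for daily monitoring after Day 6 when results trend upward. The trigger is a trend, not an out-of-range value, and the next visit is Day 14. A first High value could therefore fall between visits.
- *Blood counts.* Protocol 5.3.6 requires bi-monthly counts until lymphopenia resolves. After Month 3, haematology is scheduled at Months 6, 9, 12, 18 and 24, so the gaps are 3, 3, 3, 6 and 6 months. Counting from the Month 3 visit, a two-monthly reading gives Month 5 only (1 count before Month 6). A twice-monthly reading gives Months 3.5, 4, 4.5, 5 and 5.5 (5 counts).
- *General.* Protocol 6.4 allows safety time points to be added.
- *ECG.* No protocol trigger specifically places an ECG on an unscheduled date. Days 1 to 6 already supply 2 + 2 + 3 + 3 + 3 + 3 = 16 time points after the first dose. After Day 14 the SAP schedule shows ECGs only at Months 12 and 24.

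The SAP does not say whether triggered tests are labelled unscheduled. If they are, they cannot enter these tables.

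**4. Step per patient.** One reclassified patient moves an incidence by 100/n percentage points.

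| Arm | n | Step |
|---|---|---|
| Planned active arm | 8 | 100/8 = 12.5 |
| 27 mg arm, size not given (assumed 4 to 8) | 4 to 8 | 25.0 to 12.5 |
| Pooled placebo, if three cohorts gave 2 each (assumed) | 6 | 100/6 = 16.7 |

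**The case against.** The strongest reply has five parts.

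1. **The tables use standard shells that are not in the documents.** These may define worst case over all visits. That is possible, but an unseen shell cannot be presumed to override an explicit SAP sentence. If it does, the edit merely makes the SAP say so.

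2. **SAP 11.5.1 is more specific and may already admit all visits to 2.15 and 2.21.** The ambiguity is real for the any-visit rows. It does not reach the two QTc tables, and it does not mention unscheduled visits.

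3. **The routes are narrow.** Much of this stands. Follow-up of an abnormality already seen at a scheduled visit does not change a Low/Normal/High category, so in 2.15 and 2.21 only new abnormalities count. Lymphopenia follow-up starts from a count that is already abnormal. An extra reading at a scheduled visit keeps its nominal label and is not clearly barred.

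4. **Nothing is hidden.** Listings 24, 26, 30, 31, 33 and 34 can show the values, clinically significant abnormalities are adverse events under protocol 7.1.3, and SAP 7.1 provides separate outputs for liver events. These points limit the harm. They do not make a table of maxima contain the maximum.

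5. **Scheduled-only extremes keep ascertainment equal between arms.** This is the best argument of principle. Staff are unblinded (protocol 5.4), so discretionary sampling could differ by arm, and an arm sampled more often has more chances to show an extreme. The direction of any effect on the difference from placebo is therefore not fixed. But the SAP does not give this as its reason, and disclosing the counts per arm deals with it better than leaving out recorded values.

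**Conclusion.** The concern holds. As written, SAP 11.4.3 makes Tables 2.15, 2.18, 2.19 and 2.21 equal or understate each patient's recorded post-baseline extreme, and no stated exception prevents it. The direction for each patient is certain. The size is not known and may be zero: it depends on how many new extremes arise at unscheduled visits and on how triggered tests are labelled. There are no formal hypotheses, so no test is affected. This should be fixed because safety is the primary objective, the arms are small and the table titles promise what the rule withholds. Confidence is medium, mainly because the standard shells and the labelling practice cannot be seen.

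**What to change.** Replace the sentence in SAP 11.4.3 with:

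> Unscheduled visits are excluded from by-visit summaries and plots of means. Tables 2.15, 2.18, 2.19 and 2.21, and the any-visit post-baseline rows described in 11.5.1, use all post-baseline values, scheduled and unscheduled.

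Add a footnote to the four tables giving the number of unscheduled assessments per arm. The averaging of replicate readings in 11.5.1 stays in force. It would also help to state in 11.2.1 how event-triggered tests are labelled, though the conclusion does not rest on that.

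The cost is a short SAP edit, a filter change in four programs and one footnote, with no new data. Some safety figures may look slightly less favourable. Unequal discretionary sampling by unblinded staff could affect comparisons between arms, and the footnoted counts let the reader see whether it did.

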11.5. Appendix 5: Derived and Transformed Data

11.5.1. General

Multiple Measurements at One Time Point

 • Mean of the measurements will be calculated and used in any derivation of summary statistics but if listed, all data will be presented, including the mean. • The nominal time point will be used as described in Section 11.2. • Participants having both High and Low values for Normal Ranges at any post-baseline visits for safety parameters will be counted in both the High and Low categories of “Any visit post-baseline” row of related summary tables. This will also be applicable to relevant Potential Clinical Importance summary tables.
Study Day

 • Calculated as the number of days from randomisation date : 
 • Ref Date = Missing → Study Day = Missing • Ref Date < Randomisation Date → Study Day = Ref Date – Randomisation Date • Ref Date ≥ Randomisation Date → Study Day = Ref Date – (Randomisation Date) + 1

11.5.2. Study Population

Demographics
Age

 • GSK standard IDSL algorithms will be used for calculating age where birth date will be imputed as follows: 
 ○ Any participant with a missing day will have this imputed as day ‘15’. ○ Any participant with a missing date and month will have this imputed as ‘30th June’. • Birth date will be presented in listings as ‘YYYY’.
Body Mass Index (BMI)

 • Calculated as Weight (kg) / [Height at screening (m)]²

Extent of Exposure

 • Number of days of exposure to study drug will be calculated based on the formula: 
Duration of Exposure in Days = Treatment Stop Date – (Treatment Start Date) + 1
 • Participants who were randomized but did not report a treatment start date will be categorised as having zero days of exposure. • The cumulative dose will be based on the formula: 
Cumulative Dose = Sum of doses on Day 1 to Day 6
 • If there are any treatment breaks during the study, exposure data will be adjusted accordingly. • In the calculation of daily infusion durations gaps between the two Day 1 syringes are included, i.e. duration will be calculated as end time of infusions – start time of infusions.

11.5.3. Safety

ECG Parameters	
RR Interval	

 IF RR interval (msec) is not provided directly, then RR can be derived as : 
 [1] If QTcB is machine read & QTcF is not provided, then : $RR = \left[\left(\frac{QT}{QTcB} \right)^2 \right] * 1000$ [2] If QTcF is machine read and QTcB is not provided, then: $RR = \left[\left(\frac{QT}{QTcF} \right)^3 \right] * 1000$ If ECGs are manually read, the RR value preceding the measurement QT interval should be a collected value THEN do not derive. 	
Corrected QT Intervals	

 When not entered directly in the eCRF, corrected QT intervals by Bazett's (QTcB) and Fredericia's (QTcF) formulas will be calculated, in msec, depending on the availability of other measurements. IF RR interval (msec) is provided then missing QTcB and/or QTcF will be derived as : $QTcB = \frac{QT}{\sqrt{\frac{RR}{1000}}} \qquad QTcF = \frac{QT}{\sqrt[3]{\frac{RR}{1000}}}$ 	

Adverse Events									
General									
	
  
 AE Type	Derivations	
   
 AE Onset Time Since First Dose (Days)	 
 ➤ If Treatment Start Date > AE Onset Date : = AE Onset Date - Treatment Start Date ➤ If Treatment Start Date ≤ AE Onset Date : = AE Onset Date – Treatment Start Date + 1 ➤ Missing otherwise 	
 
 AE Duration (Days)	➤ AE Resolution Date – AE Onset Date + 1	
 
 AE = Drug-related	➤ If relationship is marked 'YES' on eCRF OR value is missing.	
  
	AE Type	Derivations	AE Onset Time Since First Dose (Days)	
 ➤ If Treatment Start Date > AE Onset Date : = AE Onset Date - Treatment Start Date ➤ If Treatment Start Date ≤ AE Onset Date : = AE Onset Date – Treatment Start Date + 1 ➤ Missing otherwise 	AE Duration (Days)	➤ AE Resolution Date – AE Onset Date + 1	AE = Drug-related	➤ If relationship is marked 'YES' on eCRF OR value is missing.
AE Type	Derivations								
AE Onset Time Since First Dose (Days)	
 ➤ If Treatment Start Date > AE Onset Date : = AE Onset Date - Treatment Start Date ➤ If Treatment Start Date ≤ AE Onset Date : = AE Onset Date – Treatment Start Date + 1 ➤ Missing otherwise 								
AE Duration (Days)	➤ AE Resolution Date – AE Onset Date + 1								
AE = Drug-related	➤ If relationship is marked 'YES' on eCRF OR value is missing.								
Adverse Events : CRS and Clinical Symptoms of Mononucleosis Definition									

 The current MedDRA version at time of database lock will be used for coding of AE's. AEs considered to be related to CRS during the first 14 days post first dose will be determined by medical expert review conducted by the GSK team. For reporting of clinical symptoms of mononucleosis, the following AE's will be extracted based on Preferred Term. In addition, other terms maybe included at the time of reporting. 									
	
  
 Reporting	Preferred Term	Verbatim Terms	
   
 Clinical	Fatigue	Feeling tired & Low energy	
  
	Reporting	Preferred Term	Verbatim Terms	Clinical	Fatigue	Feeling tired & Low energy		
Reporting	Preferred Term	Verbatim Terms							
Clinical	Fatigue	Feeling tired & Low energy							

Adverse Events		
General		
Symptoms of Mononucleosis	Malaise	Feeling unwell
	Myalgia	Joint and muscle pain & Flu like symptoms
	Oropharyngeal pain	Sore throat, throat pain
	Lymphadenopathy	Swollen glands
	Pyrexia	High temperature, Feeling hot and cold & Shivering

Laboratory Parameters

 • All BLQ values will be imputed with $\frac{1}{2}$ LLOQ. • All ALQ values will be imputed with the ALQ + [smallest positive number with the same number of decimal places as the ALQ is reported with] • Values reported as < x are assumed to have an LLOQ of x. • Values reported as > x are assumed to have an ALQ of x.

EBV				

 EBV Serology: 
 Categories (negative, positive) will be derived from absolute IgG and IgM values according to a worst case approach from absolute virus results 				
	QUEST Classification of INDEX	Quest classification of U/ml	BDR Classification of AE/mL	Unified Classification
IgG	< OR = 0.90 NEGATIVE 0.91 - 1.09 EQUIVOCAL > OR = 1.10 POSITIVE		negative : <20 positive : 20 or more	NEGATIVE POSITIVE POSITIVE
IgM	< OR = 0.90 NEGATIVE 0.91 - 1.09 EQUIVOCAL > OR = 1.10 POSITIVE	negative: <36 positive: 36 or more	negative : <20 weakly positive : 20-40 positive : 40 or more	NEGATIVE POSITIVE POSITIVE POSITIVE

 EBV Viral Load (EBVPCR_B): 
 Viral Load will also be categorized, using these groups: 
 0-1000 copies/10⁶PBM cells >1000-10000 copies/10⁶PBM cells >10000-100000 copies/10⁶PBM cells >100000 copies/10⁶PBM cells The same rules as for laboratory parameters will be applied for BLQ/ALQ values. 
Any viral load given as > XX.X or < XX.X will be treated in the same manner as described for laboratory parameters. If the result is given as not detected, then it will be imputed as 1 copies/10⁶PBM cells instead.
				

Auto-Antibodies

Positive/Negative results will be derived for all the auto-antibodies, where positive is defined as:
 
 antibody to glutamic acid decarboxylase (anti-GAD) ≥ 2.6% binding antibody to protein tyrosine phosphatase-like protein (anti IA 2) ≥ 0.44% binding Qualitative status (positive/negative status) is directly provided for islet cell antigen and will be used ZnT8 Autoantibody ≥ 1.02% binding IAA ≥ 0.6% binding 
In addition, the number of positive results at Screening (with the exception of IAA) will be derived in ADSL.

Immunogenicity

The presence of anti-drug antibodies will be summarized by positive/negative status at each time point. A participant is considered positive at a specific time point if both the Screening and the Confirming sample is positive.

The listing will show individual results for the Screening, Confirming and Titer tests. Not applicable tests will be omitted from the listing.

